### 9.7.8 Multiplicity adjustment

No formal adjustments for multiple comparisons will be performed. It should be noted that several comparisons will be made and some of the significant results may be due to chance although this is a population-based study which collects information from all MS pregnancies in FIN, SWE and NOR during the specified follow-up period.

## 9.8 Quality control

The study will be conducted as specified in this protocol. The principal investigator, the co-investigators and the sponsors of the study must approve all revisions to the protocol. All changes to the protocol shall be properly documented as protocol amendments and when necessary such protocol amendments are delivered to relevant ethics committees and register holders.

The study protocol has been written following the Code of Conduct by the European Network of Centres for Pharmacoepidemiology and Pharmacovigilance (ENCePP, 2014). The protocol also follows the key elements of the Guideline for Good Pharmacoepidemiology Practices by International Society for Pharmacoepidemiology ([www.pharmacoepi.org/resources/guidelines\\_08027.cfm](http://www.pharmacoepi.org/resources/guidelines_08027.cfm)).

EPID Research, the principal investigator, co-investigators, the sponsors and individuals acting on their behalf commit to adhere to the rules of the ENCePP Code of Conduct in their entirety. The study protocol will be registered in the ENCePP E-register of Studies ([www.encepp.eu/encepp/studiesDatabase.jsp](http://www.encepp.eu/encepp/studiesDatabase.jsp)). Study results will also be published in the ENCePP E-register.

For information on storage of records, archiving of the statistical programming performed to generate the results and possible audits, see section 9.6. Due to the study type (register study using administrative databases) on-site monitoring will not be performed.

## 9.9 Limitations of the research methods

### Exposure information

Information on patient-level data on MSDMD used in hospitals and other institutions is not included in the data from prescription databases in FIN, SWE or NOR (Furu et al 2009). This creates observation gaps and therefore there may be some cases classed as MSDMD unexposed, who are actually treated in hospitals. Some drugs are dispensed only through outpatient clinics (for example, antiretroviral drugs), and some new drug groups including some biological drugs (for example, infliximab) are mainly administered in hospitals, and are therefore not usually included in the prescription databases. Nonetheless, in FIN information on patients who have a special reimbursement for i.e. intramuscular injection, and who want to be injected by a professional instead of themselves, is included in the prescription register as the patient buys the medicine from pharmacy (personal communication with [name], SII on Finland Jan 5, 2015). In similar situation with infusion, the medicine is always obtained from the hospital pharmacy, and therefore information is not included in the Prescription Register.

In FIN, most of the MSDMDs are included in the prescription databases and are included in the study database. In FIN, SWE or NOR, IFN- $\beta$  natural (L03AB02) is not on market. Furthermore, human normal immunoglobulin (J06BA02), cyclophosphamide (L01AA01), some products of methotrexate (L01BA01, L04AX03), cladribine (L01BB04), mitoxantrone (L01DB07), alemtuzumab (L01XC04) and natalizumab (L04AA23) are on market, but they are not under the special reimbursement and are given in hospitals. Information on glatiramer acetate (Copaxone®) (L03AX13) is available since 2004, when the product was approved in EU and in NOR.

### **Study power**

The primary comparisons in this study will be performed between MS patients exposed to IFN- $\beta$  only vs. unexposed to any MSDMDs and also between women with MS exposed to IFN- $\beta$  only vs. unexposed to IFN- $\beta$  (regardless of exposure to other MSDMDs) and the study has been powered for these comparisons. The secondary objectives will also include comparisons between women with MS exposed to IFN- $\beta$  regardless of exposure to other MSDMDs vs. unexposed to any MSDMDs which will also be sufficiently powered. However, the study is not powered for comparisons made using individual pregnancy outcomes or for comparisons that only employ a subset of the cohorts in the primary comparisons.

In the power calculations, the anticipated background prevalence of serious adverse pregnancy outcomes was based on the Finnish feasibility data. Because the availability of data regarding the serious adverse pregnancy outcome varies between countries (mainly, elective termination not available in Sweden), the observed overall prevalence of serious adverse pregnancy outcomes in all of the Nordic countries might be smaller than anticipated. However, as presented in the power calculations, if the prevalence of the serious adverse pregnancy outcome is above 3%, the minimum detectable effect size is still below 2.5 (RR).

In addition, to remove any bias from Sweden, a sensitivity analysis is being done on MCAs for the Norwegian and the Finnish data including pregnancy terminations, stillbirths and live births, and another analysis including live births only.

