**Spontaneous abortion / miscarriage** refers to spontaneous loss of a pregnancy which does not comply with the definition of a birth or a spontaneous intrauterine death of a foetus, detected by a reliable prenatal diagnostic method, and the associated artificial expulsion of the foetus concerned before 22+0 GW ( $< 22+0$  GW), when the foetus weighs less than 500 grams ( $< 500$  g) according to the International Classification of Diseases, 10th revision (ICD-10) diagnosis O03 (WHO, 2014).

**Stillbirth** is birth of a foetus or a child that shows no evidence of life, but complying with the definition of a birth (22+0 GW or  $\geq 500$  g).

**Pregnancy trimesters** are divided as follows: 1st trimester 0-12 GW, 0-84 days from last menstrual period (LMP), 2nd trimester 13-26 GW, 85-182 days from LMP, 3rd trimester from 27 GW to delivery (approximately 40-42 GW), 183 days from LMP to delivery (approximately 280 days).

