cladribine	L01BB04	no	25.9.2000	19.11.1993	14.11.1996	injection no infusion yes
mitoxantrone	L01DB07	no	30.8.1993	29.10.1987	1.8.1988	yes
alemtuzumab	L01XC04	no	12.9.2013	no	no	yes
glatimer acetate (Copaxone ® )	L03AX13	yes	8.3.2004	21.9.2001	24.2.2004	no 
leflunomide	L04AA13	yes	2.9.1999	2.9.1999	5.11.2004	no
natalizumab	L04AA23	no	27.6.2006	27.6.2006	27.6.2006	yes
fingolimod	L04AA27	yes	17.3.2011	17.3.2011	17.3.2011	no
teriflunomide	L04AA31	yes	26.8.2013	26.8.2013	26.8.2013	no
azathioprine	L04AX01	yes	31.1.1968	14.3.1968	9.8.1968	no
dimethyl fumarate	N07XX09	no	30.1.2014	30.1.2014	30.1.2014	no

-  Information on only reimbursed medication can be acquired from the National Prescription Register in Finland.
-  Pre-filled syringes/pens and tablets.
-  Injection and infusion solutions - except Trexan injection solution, which is reimbursed.
-  Information on drug use in hospitals and outpatient clinics are not collected in the Prescription Registers and thus information on exposure to these types of medication is not available.
-  Some of the injections are given in hospital and some can be self-administered at home.
-  Earlier there may have been also products that have been administered in hospital.
-  Sources (accessed on 3.2.2015):  
[http://www.ema.europa.eu/ema/index.jsp?curl=pages/medicines/landing/epar\\_search.jsp&mid=WC0b01ac058001d124](http://www.ema.europa.eu/ema/index.jsp?curl=pages/medicines/landing/epar_search.jsp&mid=WC0b01ac058001d124),  
<http://www.fimea.fi/laaketieto/valmisteyhteenvetot/laakkeet>  
<http://www.lakemedelsverket.se/LMF>  
<http://www.legemiddelverket.no/Legemiddelsoek/>

**Outcome variables:** The primary (P), secondary (S) and exploratory (E) outcomes are presented here according to pregnancy timeline.

Ectopic pregnancies (S) (ICD-10: O00) and spontaneous abortions (S) (ICD-10:O03):

- Information will be obtained from Patient Register (FIN, SWE, NOR) based on hospital visits due to these diagnoses

Elective termination of pregnancy (P) (ICD-10: O04):

- Information will be obtained from the DPP (FIN) and from MBR (NOR), where the abortions are registered from GW 12.
- This information is not available from SWE.

Stillbirth (P):

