- Information will be obtained from the DPP (FIN) and MBR (SWE, NOR). The Finnish DPP and Norwegian MBR include information on all stillbirths of fetuses with a birth weight of at least 500 g or with a gestational age of at least 22+0 GW. The Swedish MBR includes data on stillbirths after 28 GW.

Live Birth (P):

- Information on live births will be obtained from the DPP (FIN) and MBR (SWE, NOR)

MCAs (P):

- Information will be obtained from the DPP (FIN), Patient Register (SWE) and MBR (SWE, NOR). The study will concentrate on MCAs. These outcomes are registered according to ICD-9 classification into 25 groups (ICD-codes 740-759). Minor anomalies will principally be excluded according to the European Surveillance of Congenital Anomalies (EUROCAT).

Defect cases (E):

- Information will be obtained from the DPP (FIN), Patient Register (SWE) and MBR (SWE, NOR). Defect cases with 3 or more minor anomalies will be defined according to the European Surveillance of Congenital Anomalies (EUROCAT).

Serious adverse pregnancy outcome (P):

- A composite endpoint including presence of elective TOPFA, MCA or stillbirth.

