**Information on elective terminations, spontaneous abortions and stillbirths**

Information on elective TOPFA is not available from SWE, while in NOR information on pregnancy terminations is available only from GW 12 onwards. Furthermore, information on spontaneous abortions is incomplete in this study, as only women treated in hospitals due to spontaneous abortions are included in the data. Usually spontaneous abortions are in the early pregnancy and women may not even know yet about the pregnancy. Therefore estimates based on hospital records lead to underestimation of the actual number of spontaneous abortions. However, it is expected, but not certain, that the underestimation of spontaneous abortions would be comparable across cohorts. Therefore, any differences observed between cohorts are likely to be due to the differences in cohort exposure. As noted in section 9.7.2, the denominator for the prevalence of MCAs includes the number of elective terminations and the number of births (still or live). Because data on elective terminations are not available in SWE, the prevalence of MCAs will be calculated first in the data from FIN and NOR. The prevalence of MCAs will then be re-calculated to include MCAs identified from SWE. However, the denominator for this prevalence will exclude the elective TOPFAs identified from FIN and NOR.

Because information on elective pregnancy terminations is not available from SWE, analyses on MCAs will be calculated including TOPFA with Finnish and Norwegian data and for births without TOPFA including data from all three countries.

Information on pregnancy terminations is available from GW 12 onwards from the Norwegian data, and therefore, information on early pregnancy terminations conducted before GW 12 could result in incomplete data. Therefore we will conduct separate analyses by trimesters on pregnancy terminations.

Information on stillbirths is available from GW 28 onwards from the Swedish data. Country-specific prevalence rates will be estimated for outcomes, where stillbirths are included as nominator, or denominator.

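### The Swedish primary composite lacks TOPFA and stillbirths before 28 weeks, but the analysis said to remove bias from Sweden covers MCA only; no composite or stillbirth RR is planned without Sweden or on shared components

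*Protocol*

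**What the plan says.** Section 9.4 defines the primary outcome as "A composite endpoint including presence of elective TOPFA, MCA or stillbirth". Section 2 counts a stillbirth as a birth without signs of life, "complying with the definition of a birth (22+0 GW or" at least 500 g).

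The sources differ by country (section 9.4):

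- **Terminations.** For Sweden, "This information is not available from SWE". They are available from Finland, and from Norway "where the abortions are registered from GW 12".
- **Stillbirths.** "The Finnish DPP and Norwegian MBR include information on all stillbirths of fetuses with a birth weight of at least 500 g" or a gestational age of at least 22+0 weeks. By contrast, "The Swedish MBR includes data on stillbirths after 28 GW".

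Section 9.7 pools individual data from the three countries. Section 9.7.3 compares cohort 1 with cohort 3, and cohort 1 with cohort 4, by log-binomial regression with country in the base model.

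Under Study power in section 9.9, the protocol notes that availability of the composite varies by country and treats this as a matter of lower prevalence. It then adds that "to remove any bias from Sweden, a sensitivity analysis is being done on MCAs for the Norwegian and the Finnish data". On stillbirths, section 9.9 says that "Country-specific prevalence rates will be estimated for outcomes, where stillbirths are included as nominator, or denominator".

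**The concern.** Study power in section 9.9 raises the problem for the composite and offers a remedy for a different outcome. In Sweden one of the three components is absent and another is truncated, and the Table 6 denominator (terminations plus births) can only be births. A country term in the regression lets the baseline prevalence differ between countries. It does not change what is being counted in each.

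This is a safety study. Suppose IFN-beta acted through anomalies that end in termination, or through foetal death between 22 and 28 weeks. Sweden could not show that part of the effect, and it would be diluted in the pooled RR. A reader who relies on section 9.9 would believe this had been dealt with for the primary endpoint.

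**Working it through.** **1. Which planned analyses reach the objective 2 RR for the composite or stillbirth?**

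- Finland and Norway only (sections 9.7.6 and 9.9): MCA in terminations, stillbirths and live births, and a version in live births only. The outcome is MCA.
- Three countries without TOPFA (section 9.9): MCA in births. The outcome is MCA.
- Country stratification in sections 9.7.6 and 9.9: tied to differing MCA follow-up.
- Objective 5 and the stillbirth paragraph of section 9.9: composite and stillbirth by country, as prevalences.
- Other sensitivity analyses bearing on the cohort comparisons (section 9.7.6): overlapping calendar period, drugs with long-term effects, hospital-exposure proxy. None restricts countries or harmonises components.

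None gives the composite or stillbirth RR without Sweden or on shared components.

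**2. The plan's own figure.** Inputs from section 9.5: 294 in cohort 1, 1270 in cohort 3, baseline p0 = 7.3%, two-sided 5%, 80% power. With variance pooled under the null and unpooled under the alternative:

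power = Φ{[(p1 − p0) − 1.96·√(p̄(1 − p̄)(1/n1 + 1/n0))] / √(p1(1 − p1)/n1 + p0(1 − p0)/n0)}

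At RR 1.72, p1 = 0.1256 and p̄ = 0.0829, so power = Φ[(0.0526 − 0.0350)/0.0207] ≈ 0.80. The stated 1.72 reproduces.

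**3. Effect on power.** Sweden's share is w = 482/1671 = 0.288. If Sweden misses a fraction s of composite events, pooled baseline = 7.3% × (1 − w·s). For s from 10% to 40% (assumption) this is 7.1% to 6.5%, and the minimum detectable RR is 1.73 to 1.77. The change is small.

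**4. Effect on the RR.** Let s be the share of the composite that Sweden cannot see, with RR = r. Let the rest have RR 1, and let exposure be split alike in each country (all assumptions).

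- Full-definition RR = (1 − s) + s·r
- Pooled RR = [(1 − w)·((1 − s) + s·r) + w·(1 − s)] / [(1 − w) + w·(1 − s)]

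| s | r | Full definition | Pooled |
|---|---|---|---|
| 10% | 2 | 1.10 | 1.07 |
| 20% | 2 | 1.20 | 1.15 |
| 40% | 3 | 1.80 | 1.64 |

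For the second row: (0.712 × 1.20 + 0.288 × 0.80)/(0.712 + 0.288 × 0.80) = 1.15. If all components share one RR and under-recording does not depend on exposure, the pooled RR is essentially undistorted.

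**5. Feasibility of the added analyses.**

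- *Finland and Norway:* 777 + 412 = 1189. Cohort 1 is 1189 × 0.22 × 0.8 ≈ 209, cohort 3 is 1189 × 0.76 ≈ 904, and cohort 4 is 1189 × 0.78 ≈ 927. The minimum detectable RR is 1.87 for cohort 1 vs 3 at 7.3%, and 1.93 for cohort 1 vs 4 at 6.5%. Power at RR 1.72 (cohort 1 vs 3, baseline 7.3%) falls from 80% to about 68%.
- *Three countries, shared components:* if 10, 20, 30 or 40% of composite events are dropped (assumption), baseline is 6.6, 5.8, 5.1 or 4.4%, and the minimum detectable RR is 1.76, 1.82, 1.89 or 1.98. Cohort sizes are kept at 294 and 1270; leaving out terminations would reduce them somewhat.

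**The case against.** The strongest reply is that the existing remedies reach most of the composite. The Finland and Norway MCA analysis includes terminations, and section 2 counts terminations for severe MCA as MCA. It is therefore close to the composite without stillbirths that have no anomaly, and an effect through terminated anomalous pregnancies should show there. Section 9.9 also plans a births-only MCA analysis in all three countries, and composite prevalences by country are planned, from which a crude Finland and Norway RR could be computed. The Swedish gaps are disclosed, and detail is deferred to the statistical analysis plan.

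Much of this stands, and it limits the point. What it does not supply is an adjusted RR for the primary composite or for stillbirth, and stillbirth without an anomaly is left uncovered. Nor is this only detail for the analysis plan, because the protocol itself states that bias from Sweden is removed.

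Two stronger readings may tempt a reader:

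- *That Swedish losses between 22+0 and 28 weeks vanish from the study.* This is not documented. Swedish spontaneous abortions come from the Patient Register by diagnosis code, and section 9.2.4 says gestational age is not available for them. Such a loss might be counted as a spontaneous abortion. Either way it falls outside the composite.
- *That the pooled RR mixes exactly two endpoints, so that dropping Sweden gives one common definition.* Finland and Norway also differ. Norwegian terminations start at week 12, and MCA follow-up is 12 months in Finland, 6 months in Sweden and usually at least 4 days in Norway.

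**Conclusion.** The point holds as a gap in the sensitivity analyses and an overstated sentence. The Swedish composite differs in two of its three components, and the analysis said to remove bias from Sweden does not estimate the primary RR.

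A reader might infer that the primary RR is biased or the power calculation wrong. The document supports neither. The 1.72 reproduces, and power barely moves under the assumed losses. Distortion of the RR requires that the components unseen in Sweden have a different RR from the rest, or that their under-recording depends on exposure. Section 9.7.6 concedes the second possibility for TOPFA and MCA. The share of the composite that Sweden cannot see is not given, so the size cannot be derived, and the figures in the table are illustrations only. The change is worth making because the data are already held and it would show whether the primary result depends on the Swedish definition.

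**What to change.** In section 9.7.6, for cohort 1 vs 3 and cohort 1 vs 4:

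- Extend the planned Finland and Norway sensitivity analysis to the RRs for the composite and for stillbirth from 22+0 weeks or 500 g.
- Add a three-country composite limited to components recorded everywhere: MCA in births plus stillbirth from 28 weeks, with births as denominator. Finnish and Norwegian stillbirths below the threshold leave both numerator and denominator; those registers hold gestational age. Settle whether the Swedish limit is after 28 weeks (section 9.4) or from week 28 onwards (section 9.9).
- Report both beside the pooled RR. State that they harmonise TOPFA availability and the stillbirth threshold, but not Norwegian terminations before week 12 or the differing MCA follow-up. State also that the births-only version cannot see effects acting through TOPFA in any country.

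Under Study power in section 9.9, reword the sentence on Sweden so that it claims only to address bias in the MCA outcome.

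The cost is a few extra models on data already held and a wording change. Intervals will be wider: a minimum detectable RR of about 1.87 instead of 1.72 in Finland and Norway, which is acceptable for a sensitivity analysis.

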### **Variation in MSDMD use between countries**

There is variation between the countries regarding MSDMDs on market. Some of the products are not on market and some of the products are new on market. For example, teriflunomide was licensed in the European Union in 2013. New MS immunomodulatory therapies (e.g. cladribine, mitoxantrone and teriflunomide) can have long-term side effects. Although we are not able to evaluate the long-term effects of these newer MSDMDs in this study, we are reporting the proportion of pregnancies in different groups that are using these treatments with respective treatment duration and duration of unexposed period at LMP. We will also perform separate sensitivity analyses that adjust for exposure of these treatments and their duration.

### **Information on MS disease**

It is known that there are regional and international differences in prevalence and incidence of MS. As for information on age at MS onset, disease status, and disease severity are not available from all MS data sources of these countries, the effect of MS and MSDMDs on these pregnancy outcomes in patients with different types of MS cannot be distinguished in this study. Therefore, confounding by indication is possible.

MS is more prevalent in Northern European countries than in southern part of Europe. It is unlikely that drug-related effects are due to the prevalence of the disease, but the large study population increases the likelihood of observed rare adverse outcomes. Information on country and region will be included in the descriptive, multivariate, as well as sensitivity analyses in this study.

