### 9.7.3 Analysis of primary objectives

With regard to objective #1, the descriptive statistics including the number of events (n) and prevalence (%) will be presented for each pregnancy outcome (i.e. serious adverse pregnancy outcome, elective TOPFA, MCA, stillbirth, and live birth) in each study cohort separately and also for the whole study population. Information on live births, stillbirths and TOPFAs will be included in the analyses of MCA, as approximately 10% of MCAs are detected in foetuses of TOPFA.

With regard to objective #2, the prevalence of the serious adverse pregnancy outcomes will be compared between the study cohorts using log-binomial regression. Two models, base and adjusted, will be used in these comparisons. The base model will be adjusted for the following design variables and *a priori* likely confounders: country, year of pregnancy outcome, maternal age at LMP, number of previous pregnancies, any chronic diseases, and exposure to any teratogenic medications including steroids.

The adjusted model will be built using a variable selection procedure (Bursac et al. 2008). Candidate covariates for the adjusted model will be those in the base model and the following additional ones: university hospital district, pre-pregnancy weight, pre-pregnancy BMI, number of previous abortions, smoking status during pregnancy, number of foetuses in pregnancy (single vs. multiple), time since MS diagnosis and duration of MS treatment as available in the data sources. Variable selection starts by applying first the unadjusted model and proceeds as follows:

1. Each candidate covariate will be considered a potential confounder if the univariate association between the covariate and the serious adverse pregnancy outcome, tested with the Wald test for logistic regression with *P*-value cut-point of 0.25.
2. All candidate covariates identified as potential confounders in step 1 will be added simultaneously to the model. After this, additional covariates not identified as potential confounders in step 1 will be added to the model one at a time and the model fit comparing each null vs alternative model will be assessed by the likelihood-ratio test. Variables in the alternate model will be retained at a likelihood ratio test of *P*-value <0.1.

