### 9.7.6 Sensitivity analyses

- Lack of information on terminations of pregnancy due to foetal anomalies from SWE may yield underestimation of the prevalence of MCA in the study population. In FIN, 10.5% of total cases with MCAs were diagnosed and recorded in TOPFAs between 1993 and 2010. However, this may bias the study results on MCAs if the risk for TOPFA differs between women with different MSDMD exposures or MS exposure in SWE. Separate analyses will be performed on MCAs for the Norwegian and the Finnish data including pregnancy terminations, stillbirths and live births, and another analysis including live births only. The analyses will also be stratified by country as the follow-up times of the newborn babies for recording the malformations in MBRs or Malformation Register may vary between the countries.

- Information on pregnancy terminations is available from GW 12 onwards from the Norwegian data, and therefore, information on early pregnancy terminations conducted before GW 12 could result in incomplete data. Therefore separate analyses by trimesters on pregnancy terminations will be performed.
- In additional sensitivity analyses on MCAs, outcomes will be assessed where exposure occurred prior to pregnancy and through to the end of the first trimester of pregnancy. Also, an analysis of MCA outcomes from live births only will be performed.
- As there is a geographical variation in MS prevalence not only between countries but also within countries, descriptive statistics will be conducted by country and university hospital district level. Country and region will also be included in the multivariate analyses.
- Possible changes in diagnostic criteria and developments in examination and treatment throughout time, as well as trends in obstetric care may influence the estimated prevalence. The study periods also vary between the countries, which may reflect the deviation in the results. Therefore the year of pregnancy outcome will be taken into account in the descriptive statistics and analyses. By taking into account the data from 1 Jan 2005 to 31 Dec 2014 from each country (time period in which the data is available i.e. overlaps for all 3 countries), a separate sensitivity analysis of the primary objective will be provided as well.

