### **Relevance of results to the European IFN- $\beta$ Pregnancy Registry**

Results of this retrospective cohort study are not directly comparable with the information derived from the European IFN- $\beta$  Pregnancy Registry. Available information on disease severity and other confounding factors differs between the health registers and the European IFN- $\beta$  Pregnancy Registry and in some cases is missing, such that the rates cannot be adjusted to be comparable. In addition, the pregnancy cases included in the Nordic health registers are population-wide and are not based on a sample, whereas the European IFN- $\beta$  Pregnancy Registry is based on spontaneous reports.

Furthermore, study and exposure periods differ between the countries in this study and follow-up periods in the European IFN- $\beta$  Pregnancy Registry. Also, it is known that there are regional and international differences in MSDMD treatment practices, MSDMDs on market and prevalence of MS. With the available data in this study we aim to partially control for some of these variations by stratification and adjustment for country, hospital district, year of pregnancy outcome, maternal age at LMP, time since MS diagnosis and duration of IFN- $\beta$  treatment.

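### Sections 9.7.6 and 9.9 state that country and region will be in the multivariable analyses, but 9.7.3 never fixes district in any model and lets country be dropped from the adjusted model by a P-value or the 1:10 cap

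*Protocol*

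**What the plan says.** Three places in the protocol describe geographic adjustment.

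- Section 9.9, under the heading on MS disease information: "Information on country and region will be included in the descriptive, multivariate, as well as sensitivity analyses in this study".
- Section 9.7.6: "Country and region will also be included in the multivariate analyses". The sentence before shows what region means: "descriptive statistics will be conducted by country and university hospital district level".
- Section 9.9, on relevance to the European registry, more softly: the aim is partial control "by stratification and adjustment for country, hospital district, year of pregnancy outcome" and other factors.

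Section 9.7.3 specifies the models. The base model is adjusted for "country, year of pregnancy outcome, maternal age at LMP, number of previous pregnancies, any chronic diseases, and exposure to any teratogenic medications including steroids". District is not in that list. For the second model, "Candidate covariates for the adjusted model will be those in the base model and the following additional ones: university hospital district", followed by seven more variables. Selection starts from the unadjusted model:

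- Step 1 screens each candidate with a univariate Wald test at 0.25. Step 2 then begins: "All candidate covariates identified as potential confounders in step 1 will be added simultaneously to the model". The remaining candidates are tried one at a time and kept at a likelihood-ratio P<0.1.
- Step 3 reduces the model at P<0.1.
- Step 4 caps it at one covariate per ten outcomes if outcomes are few, and omits the least significant covariates. No variable is exempt.

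**The concern.** The statements in 9.7.6 and 9.9 carry no condition, and 9.9 names multivariable and sensitivity analyses separately, so they cannot be read as describing a sensitivity analysis only. Yet no model in 9.7.3 is certain to contain both terms. The base RR is never adjusted for region, and the adjusted RR may contain neither term.

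Losing country matters more. Section 9.7.3 itself introduces the base covariates as design variables or likely confounders, and country fits the first description. It reflects how the composite is captured:

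- Sweden has no register of terminations, so no TOPFA.
- Norway records terminations only from gestational week 12.
- Swedish stillbirths are recorded only after week 28.
- Malformation follow-up is 12 months in Finland, 6 months in Sweden and usually at least 4 days in Norway.

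These differences are known in advance, so a data-driven test is the wrong way to decide whether to adjust for them. The selection steps also have no defined way to handle two factors of which one is nested in the other.

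**Working it through.** **1. What each model guarantees.**

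| | Country | District |
|---|---|---|
| 9.7.6 and 9.9 | included | included |
| 9.7.3 base model | fixed | absent |
| 9.7.3 adjusted model | candidate | candidate |

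**2. The cap.** The anticipated sizes of cohorts 1 and 3 (section 9.5) give 294 + 1270 = 1564 pregnancies. At 7.3% that is 0.073 × 1564 ≈ 114 outcomes, so 11 covariates. At 3%, the lowest prevalence in 9.5, it is 0.03 × 1564 ≈ 47 outcomes, so 4. Section 9.7.3 lists 6 + 8 = 14 candidates, so the cap can bind. If district levels are counted singly, 9 to 16 districts (the number is not in the protocol) would use 8 to 15 terms.

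**3. How often country fails the test.** I split 1564 pregnancies in the ratio 777:482:412 from 9.5, assumed recorded prevalences of 7.3% in Finland and 4–5.5% in Sweden and Norway, and applied the likelihood-ratio test of country (2 df) alone. It misses P<0.1 in about 18% of runs at 7.3/4/4% and about 65% at 7.3/5.5/5.5%. A real difference in capture is therefore often discarded.

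**4. Nesting.** Each district lies in one country, so the country columns are sums of district columns. With fixed dummies for both, the design matrix has rank 10 of 12, 16 of 18 and 17 of 19 columns for 9, 15 and 16 districts, always short by 2. The likelihood-ratio test of country given district thus has 0 df and cannot show P<0.1. If country is removed on that ground, district is tested alone with all its degrees of freedom.

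- Ignoring step 1, geography is then lost although country alone would have been kept in about 20–31% of runs (15 or 16 districts).
- Requiring district to pass the 0.25 screen first cuts this to about 9–16% if the screen uses a likelihood-ratio P, and to about 2–9% with an approximate Wald test (9 to 16 districts). The Wald test is the one 9.7.3 names.

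**5. Does aliasing change the exposure effect?** No. In one simulated data set the exposure coefficient was −0.1331 and the log-likelihood −331.783, both with country plus district and with district alone.

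**6. Bias if country is lost.** With n pregnancies, exposure share e and risk p in each country, and no true effect:

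RR = [Σ n·e·p / Σ n·e] ÷ [Σ n(1−e)p / Σ n(1−e)].

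Take n = 777, 482, 412 and p = 7.3%, 4%, 4%. Let e be 294/1564 = 18.8% in Finland and 18.8 × 23/24 = 18.0% in Sweden. The factor follows section 9.5, where 76% and 77% are unexposed to any MSDMD, so 24% and 23% are exposed. Norwegian exposure is an assumption.

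- Norway 10%: exposed 15.78/274.0 = 5.76%; unexposed 76.70/1397.0 = 5.49%; RR = 1.05.
- Norway 35%: exposed 19.90/377.0 = 5.28%; unexposed 72.58/1294.0 = 5.61%; RR = 0.94.

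Using the any-MSDMD shares of 24% and 23% directly moves the range to about 0.97–1.07. With Norway also at 24% the RR is 1.00.

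**7. Scale.** The protocol's minimum detectable RR of 1.72 reproduces (1.720 with 24/331, 294 and 1270, 80% power, two-sided 5%). It is not affected by this point.

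**The case against.** The strongest reply is that this is mostly a matter of wording. The base model is always fitted and always holds country. Country-stratified analyses are planned in 9.7.6 and 9.9. The registry paragraph states an aim of partial control, and covariates are used only as available. The coding of nested factors can be left to the separate analysis plan. All of this stands. It limits the point to the adjusted model and to the plain conflict between sections. It does not remove the conflict, because the protocol itself fixes the candidate list, thresholds and cap, and an analysis plan that follows 9.7.3 inherits them.

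The reply also notes that step 3 sets no order of removal and that a 0-df comparison gives no P-value. Testing district given country first would keep country. That is right: the rule is undefined here, and the loss in item 4 is one possible outcome.

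A reader might infer that entering country and district together makes the model singular and so destroys all geographic adjustment. The documents do not support this. District terms already span country, R (the stated software) normally drops redundant columns, and the exposure RR is unchanged. A missing-district level shared across countries, which the rule in 9.7.7 could create, would even restore full rank, though country would then be identified only by records lacking a district.

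A reader might also infer that the adjusted RR is seriously confounded by register capture. The near-equal exposure shares in Finland and Sweden speak against it. A larger bias from regional confounding in the base model would need a correlation between district risk and IFN-β use for which the protocol gives no figure.

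**Conclusion.** The inconsistency holds. Sections 9.7.6 and 9.9 state that country and region will be in the multivariable analyses, while 9.7.3 fixes only country, only in the base model, and leaves both to selection in the adjusted model. The main weakness is that a known design variable can leave the adjusted RR through a low-powered test (about 18–65% of runs under the assumed prevalences) or through the cap. Nesting adds a smaller, order-dependent loss (about 2–16%).

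The consequence for the estimate is probably modest, an RR of about 0.94–1.05 under no effect. That rests on assumed Norwegian exposure of 10–35%, assumed prevalences outside Finland, and similar exposure in Finland and Sweden. The case for change is that the plan should do what it says and that the repair is cheap. A large expected bias is not part of it.

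**What to change.** In 9.7.3, state that country is forced into the adjusted model as well as the base model, and is exempt from steps 1–3 and from omission under the 1:10 cap. Remove university hospital district from the list of fixed-effect candidates so that it does not compete with country. If regional adjustment is wanted, add district within country in a named sensitivity analysis, for example as a random intercept. Reword 9.7.6 and both paragraphs of 9.9 to match.

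The cost is a few sentences, two degrees of freedom for country in the adjusted model and slightly wider intervals. The sample size section does not change.
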